# (11) Analysis of metabolites

Metabolites of BB102 will be identified. The metabolites and subjects will be tabulated.

# (12) Subgroup analysis

Subgroup analysis will be performed by gender.

# (13) Interim analysis

Not applicable.

# **Study Flow Chart**

Period	Screen ing period/ baselin e		Single	e-dosii	ng per	iod*		Multiple-dosing period						Follow	-up period
Time (days)	D-28 to D-1	D1	D2	D3	D4	D5		The 1st cycle  The 2nd the 2nd cycle cycle				the 2 nd	Within	Safety visit	Subsequent follow-up
Per multiple-dosing time (days)							C1D1	C1D8 (出 day)	C1D15 (±1 day)	C1D21 (土 day)	C2D1 (±1 day)	CnD21 (±3 days)	7 days after the last dose	(17 -1)	Follow-up once every 8 weeks (#7 days) after the last dose
Informed consent 	X														
Reviewing inclusion/exclusion criteria	X														
Demographics 	X														
Medical history and medication history 	X														
Hematology 	X					X		Xa	Xa	Xa		Xb	X d	X d	
Urinalysis 	X					X		Xa	Xª	Xª		Xc	X d	X d	
Stool routine 	X					X (±1 day)		Xª	Xa	Xa		X c	X d	X d	

Period	Screen ing period/ baselin e		Single	-dosii	ıg per	iod*		Multiple-dosing period						Follow	Follow-up period		
Time (days)	D-28 to D-1	D1	D2	D3	D4	D5		The	1 st cycle		The 2 nd cycle	From the 2 nd cycle	the 2 nd	the 2 nd	Within	Safety visit	Subsequent follow-up
Per multiple-dosing time (days)							C1D1	C1D8 (±1 day)	C1D15 (±1 day)	C1D21 (±1 day)	C2D1 (出 day)	CnD21 (±3 days)	7 days after the last dose	28 days (±7 days) after the last dose	Follow-up once every 8 weeks (#7 days) after the last dose		
Blood biochemistry 	X					X		Xa	Xa	Xa		Xb	X d	X d			
Coagulation 8	X					X		Xa	Xa	Xa		Xb	$X^{d}$	X d			
Vital signs 	X	X		X		X	X	X	X	X		Xb	X				
12-lead ECG 	X	X		X		X	X	X	X	X		Xb	X				
Physical examination 11	X					X		X	X	X		X b	X				
ECOG assessment	X					X				X		Xc	X				
Pregnancy-related test 12	X									X		X c	X				
Echocardiography 13	X									X		X	X				
Serum etiological test 	X																

Period	Screen ing period/ baselin e		Single	-dosii	ng per	iod*		N	Iultiple-do	osing perio	od		End of treatme nt visit (EOT)	Follow	-up period
Time (days)	D-28 to D-1	D1	D2	D3	D4	D5	The 1st cycle				The 2 nd cycle	From the 2 nd cycle Wi	Within	Safety visit	Subsequent follow-up
Per multiple-dosing time (days)							C1D1	C1D8 (土 day)	C1D15 (±1 day)	C1D21 (±1 day)	C2D1 (±1 day)	CnD21 (±3 days)	7 days after the last dose	28 days (±7 days) after the last dose	Follow-up once every 8 weeks (#) days) after the last dose
Study drug administration		X					Adı		ion of BB1 schedu once daily	ıled as:		tively			
Dispensing/collectin g diary cards and drugs							X			X		X	X		
Tumor assessment 15	X									X		X	X		X
Detection of biomarkers 	X								X			X	X		X
PK blood sampling		X	X	X	X	X	X	X	X	X	X				
Blood sampling for identification of metabolites 		X	X	X	X	X									

Period	Screen ing period/ baselin e		Single	e-dosii	ng per	iod*	Multiple-dosing period					End of treatme nt visit (EOT)	Follow	-up period	
Time (days)	D-28 to D-1	D1	D2	D3	D4	D5	The 1st cycle 2nd			The 2 nd cycle	From the 2 nd cycle	Within	Safety visit	Subsequent follow-up	
Per multiple-dosing time (days)							C1D1	C1D8 (土 day)	C1D15 (±1 day)	C1D21 (±1 day)	C2D1 (±1 day)	CnD21 (±3 days)	7 days after the last dose	28 days (±7 days) after the last dose	Follow-up once every 8 weeks (#) days) after the last dose
Anti-tumor treatment and survival information after the end of study treatment 														X	X
Adverse event 	X	X												X	
DLT evaluation *			X							X					
Concomitant medication 		XX													
Inpatient nutrition assessment (NRS-2002)		Assessed as needed													

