### Subsequent follow-up visits [once every 8 weeks (± days) after the last dose]:

Specific procedures and assessments are as follows:

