# 8.1.2 Collection and reporting process of AEs

#### **AE** collection period

AEs will be collected from the first dose of investigational product to 28 days after the last dose of investigational product or the start of new anti-tumor therapy (whichever occurs first). During the AE collection period, all AEs should be reported in the source medical record and the eCRF. After the AE collection period, only the existing AEs, newly occurred AEs definitely related/possibly related/possibly unrelated to the study drug/ucertain, and AEs leading to death will be recorded. For AEs still existing after the end of study treatment, if they are related to the study treatment, they will all be followed up until resolution, stabilization, death, loss to follow-up or it is reasonably explained.

All adverse medical events that occur during the period from subject's signing of the ICF to the first dose of the investigational product will be recorded as medical history instead of being recorded as AEs, unless they meet one of the following conditions:

- Any adverse medical event related to procedures specified in the clinical study protocol (e.g., bruising caused by blood sampling for laboratory test, etc.);
- Adverse medical events caused by treatment discontinuation related to clinical study protocol (e.g., change or discontinuation of prior concomitant medications).

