#### **AE** reporting

At each study visit, the investigator will assess whether there is a subjective AE. A neutral question can be asked, such as "How do you feel since the last visit?".

All clinically significant laboratory abnormalities confirmed by repeated laboratory test will be followed-up until these abnormalities are resolved to acceptable level or satisfactory explanation is given.

For all AEs, no matter stated by the subject, asked out by the investigator or found out by physical examination, laboratory test or other methods, they should all be recorded in the source medical records and the eCRF completely no matter regardless of being related to the study drug as considered by the investigator. The following information will be recorded for AEs:

Event term.

- Start and end date.
- Severity.
- The investigator's judgment on the causal relationship between the AE and the study drug.
- Relevant actions taken with the study drug.
- Treatment or interventional measures taken for AEs.
- Event outcome.
- SAE or not.

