# Further explanations for SAEs are as follows:

- a. Any death occurring during the study period or within 28 days after the last dose, including those completely unrelated to the study drug. If the patient dies during the study period and an autopsy is conducted, the investigator should provide the sponsor and the Ethics Committee with other necessary information, such as autopsy report and final medical report.
- b. Occurrence of AEs causes immediate risk of death for the patient. These do not include AEs that may cause death after serious progression, e.g., drug induced hepatitis without liver failure.
- c. Any AEs resulting in hospitalization or prolongation of existing hospitalization (prolongation of existing hospitalization means the planned or expected discharge is delayed, usually after staying overnight in the hospital for at least one day). These do not include elective surgeries or examination before admission decided before the study, with no change of treatment course during the study.
- d. Any AEs causing injury, damage or destruction of patient's function and/or physiological structure, physical activity or quality of life.
- e. It is suspected that exposure of parent to the study drug may cause adverse outcome of descendants.
- f. Medical and scientific judgment must be exercised in deciding whether expedited reporting is appropriate in other situations, such as important medical events that may not be immediately life-threatening or result in death or hospitalization but may be considered serious if medical intervention is necessary to prevent one of the above situations. For example, intensive therapy in the emergency room or allergic bronchospasm at home, blood dyscrasia or convulsion not resulting in inpatient hospitalization, or those leading to drug dependence or drug abuse.

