#### Death

All death events that occur during administration period or within 28 days after the last dose must be reported to the sponsor/CRO's safety department within 24 hours, and the death causes should be recorded in proper areas in the eCRF and the SAE report. If the death is jointly caused by multiple reasons, the investigator must determine the main cause of the death. The report should include information on AE condition, major or minor causes of death (if any), etc. In case of reports involving death events, the investigator should provide the sponsor/CRO and the Ethics Committee with other necessary information, such as autopsy report and final medical report.

Note: Generally, disease progression (including progressive symptoms and signs) should not be reported as an AE or SAE, but it should be reported as an SAE (with the severity as grade 5) if the patient's death is due to his/her disease progression (and the death can not be included as any of the grade 5 AEs in CTCAE).

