### 8.3.2 Collection and reporting of SAEs

Except for the SAEs unnecessary to be reported immediately as per the trial protocol or other documents (e.g., Investigator's Brochure), the investigator should report all the SAEs to the Sponsor/CRO in writing immediately, and thereafter provide a detailed and written follow-up report in a timely manner.

For any SAE in the trial, regardless of whether it is related to the study drug or not, the investigator should provide timely rescue treatment, complete the *Serious Adverse Event Reporting Form* within 24 hours of awareness, sign and date it and report it to the sponsor/CRO.

For initial SAE report, the investigator should record in detail about the report source, basic information of the subject, name of the study drug, SAE name, SAE symptoms/vital signs/examination indicators, start and end date, severity, treatment time, actions taken, causal relationship with the study drug and outcomes, etc., and ensure that the record is true, accurate, complete, timely and legal. After the initial report, the SAE should be continuously followed up and relevant new information or updated information of the previous report should be reported in the form of follow-up report timely (the follow-up report should be reported within 24 hours after obtaining the new information).

The investigator must provide causality assessment when reporting SAEs. If the investigator can not confirm whether the AE is an SAE, it will be considered as an SAE before proving its nature.

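### The follow-up safety visit may take place from day 21 although AE collection runs to day 28 after the last dose, and the schedule has no later laboratory test or AE item to cover the difference

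*Protocol*

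**What the plan says.** The flow chart sets the safety visit at "28 days (±7 days) after the last dose". Section 4.3.5 lists its content as hematology, urinalysis, stool routine, biochemistry, coagulation, AEs, concomitant medications, and later anti-cancer therapy and survival. Laboratory results from anywhere in the visit window are accepted.

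Section 8.1.2 fixes the collection period: "AEs will be collected from the first dose of investigational product to 28 days after the last dose of investigational product", or to the start of new anti-tumor therapy if that comes first. After that period, existing AEs continue to be recorded, as do "newly occurred AEs definitely related/possibly related/possibly unrelated to the study drug/ucertain, and AEs leading to death will be recorded".

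The next contact in Section 4.3.5 is headed "Subsequent follow-up visits [once every 8 weeks", with a window of ±7 days. Its list covers tumor assessment, biomarkers, anti-cancer therapy, survival and nutrition. It has no AE item and no safety laboratory test, and the AE row of the flow chart has no mark in that column. The AE reporting text in Section 8.1.2 nevertheless says: "At each study visit, the investigator will assess whether there is a subjective AE".

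Deaths and SAEs have routes of their own. Section 8.3.1 counts as an SAE "Any death occurring during the study period or within 28 days after the last dose, including those completely unrelated to the study drug". Under its Death heading, "All death events that occur during administration period or within 28 days after the last dose must be reported" within 24 hours. Section 8.3.2 applies 24-hour reporting from awareness "For any SAE in the trial, regardless of whether it is related to the study drug or not".

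**The concern.** The protocol defines a 28-day post-dose period for complete AE collection, then allows the visit that should close it to come a week early. The end-of-treatment visit does not help, because it falls within 7 days of the last dose. AE and SAE incidence is a primary endpoint of the escalation (Section 7.1) and a secondary endpoint of the expansion (Section 7.2).

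If ascertainment in the last post-dose week depends on when a visit happens to be booked, subjects with identical experience can contribute different AE counts, and any event that is missed can only lower the incidence. Laboratory changes are the more exposed part. Clinically significant ones count as AEs (Section 8.1.1), the liver is the main toxic target organ in both animal species (Section 1.5.3), and enzyme or bilirubin changes are found by testing rather than by asking.

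**Working it through.** The plan states no figure to reproduce. The check is visit-window arithmetic followed by a comparison of sections.

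**Inputs.** Safety visit at 28 ±7 days (flow chart). AE collection to day 28 (Section 8.1.2). Subsequent visits every 8 weeks ±7 days after the last dose (Section 4.3.5). Data cut-off 8 weeks after the last subject starts treatment (Section 4.7). Follow-up ends at cut-off (Section 4.3.5, notes a and b).

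**1. Permitted safety visit days.** 28 − 7 = 21 to 28 + 7 = 35. That is 15 days, of which 7 (days 21–27) precede day 28.

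**2. Post-dose days left after the visit.** For a visit on day d, this is max(0, 28 − d).

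| Visit day | Days left | Share of 28 |
|---|---|---|
| 21 | 7 | 7/28 = 25% |
| 24 | 4 | 4/28 = 14.3% |
| 27 | 1 | 1/28 = 3.6% |
| 28–35 | 0 | 0% |

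The protocol does not say how visits will be spread over the window. If they were spread evenly (an assumption, for illustration only), the mean would be (7+6+5+4+3+2+1)/15 = 28/15 = 1.9 days, or 1.87/28 = 6.7% of the post-dose period.

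**3. Next scheduled contact.** 56 ± 7 = days 49–63, which is 49 − 21 = 28 to 63 − 21 = 42 days after a day-21 visit. An event on days 22–28 would then be asked about between 49 − 28 = 21 and 63 − 22 = 41 days after it occurred, and no laboratory sample is scheduled in between.

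**4. Subjects with no later visit.** The earliest subsequent visit is 49 days after the last dose. Anyone whose last dose is less than 49 days before cut-off cannot reach one. For the last subject enrolled, cut-off is 56 days after starting, so this applies to any last dose later than 56 − 49 = 7 days after starting. If that last dose is also no later than 56 − 28 = 28 days after starting, the whole 28-day AE period still falls before cut-off. A day-21 visit can then be the final scheduled contact.

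**5. Schedule against Section 8.** The AE reporting text requires AE assessment at each study visit and makes no exception for follow-up. The flow chart and the visit list in Section 4.3.5, which sites use to run visits, leave it out of the 8-week visits. The two must be reconciled.

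**The case against.** A reader might infer that the last quarter of the safety window goes unobserved, deaths and SAEs included, because no later visit asks about AEs. The protocol does not support that reading, for four reasons.

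- The AE reporting text requires enquiry at every study visit, with a sample question covering the time since the last visit. A subject seen on day 21 and again near day 56 should be asked about days 22–28. What is missing is the item in the schedule, not the obligation.
- The collection period ends by day count, not at the safety visit. After day 28, new AEs of any causality except definitely unrelated are still recorded. Section 4.3.6 also allows unscheduled visits when clinically needed.
- Deaths within 28 days have their own 24-hour report, and survival is recorded at every subsequent follow-up visit. SAEs are reported on awareness rather than by visit.
- The AE period starts at the first dose. Seven days is at most 25% of its 28-day tail, and a share of days is not a share of events. DLT assessment runs only to the end of Cycle 1, so it is essentially unaffected.

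It can also be said that ±7 days is an ordinary scheduling tolerance, that the protocol promises no laboratory surveillance to day 28 exactly, and that where new anti-tumor therapy starts early an early visit is appropriate.

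Most of this stands and sets the limits of the point. It does not remove the point. Enquiry three to six weeks later is weak for minor events and cannot recover a transient laboratory change. Some subjects have no later visit at all. Learning of a non-fatal SAE may itself depend on contact.

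**Conclusion.** The point holds in a limited form, as a minor defect of schedule. A compliant safety visit can precede the end of AE collection by up to 7 of the 28 post-dose days. No safety laboratory test follows it, and the schedule omits the later AE enquiry that Section 8.1.2 requires. The events at risk are mainly non-fatal, non-serious AEs and laboratory abnormalities on days 22–28.

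The 25% is the worst case, for a subject seen on day 21 who has not started new anti-tumor therapy. The gap is nil for visits on or after day 28. Any missed events would lower AE incidence, but the protocol gives neither the distribution of visit days nor post-dose event rates, so the size cannot be computed and is probably small. The statement that some subjects have no later visit assumes that follow-up stops at data cut-off, as the notes to Section 4.3.5 say.

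**What to change.** Make three edits:

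1. In the flow chart and Section 4.3.5, set the safety visit window to 28 (+7) days, with an earlier visit only if new anti-tumor therapy starts.
2. State that if a visit is nevertheless held before day 28, AE and SAE enquiry is completed by telephone on or after day 28. This covers enquiry only. Late laboratory changes are addressed by the first edit.
3. Add an AE item to the subsequent follow-up visits in the flow chart and Section 4.3.5, so that both agree with the AE reporting text in Section 8.1.2.

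The cost is slightly less scheduling freedom and an occasional telephone call. No routine visit or sample is added. The change belongs in the protocol, because analysis cannot recover events that were never collected.

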# **Note:**

1. Informed consent: Subjects should sign an informed consent form (ICF) before starting any study-related procedure.

- **2. Demographics:** Age, gender, race and ethnicity.
- **3. Medical history and medication history:** History of all neoplastic diseases, history of all anti-tumor therapies, history of other diseases (within 6 months before enrollment and at present), history of other medications (within 6 weeks before enrollment and at present), family history, surgical history, allergic history, smoking history, history of drug abuse/dependence and history of menstruation and childbearing.
- **4. Hematology:** Red blood cell (RBC) count, white blood cell (WBC) count, absolute monocyte count (ABMONO), platelet (PLT) count, absolute neutrophil count (ANC), absolute lymphocyte count (ABLYMP), basophil count, absolute eosinophil count (ABEOS), absolute reticulocyte count (ABRETIC), neutrophil percentage, hemoglobin (Hb), hematocrit (HCT), mean corpuscular volume and mean corpuscular hemoglobin concentration (MCHC). Hematology test at screening visit should be completed within 7 days prior to the first dose, and abnormal test parameters with clinical significance can be re-tested once within 7 days as needed.
- 5. Urinalysis: Potential of hydrogen (pH), specific gravity, urine RBC, urine WBC, urine glucose, urine bilirubin, urine protein, urobilinogen, urine ketone bodies and urine occult blood. Urinalysis at screening visit should be completed within 7 days prior to the first dose, and abnormal test parameters with clinical significance can be re-tested once within 7 days as needed.
- **6. Stool routine**: Color, shape, fecal RBC, fecal WBC, fecal occult blood, fecal choline and fecal bilirubin. Stool routine test at screening visit should be completed within 7 days prior to the first dose, and abnormal test parameters with clinical significance can be re-tested once within 7 days as needed.
- 7. Blood biochemistry:
  - 1) **Liver function**: aspartate aminotransferase (AST), alanine aminotransferase (ALT), alkaline phosphatase (ALP), lactate dehydrogenase (LDH), γ-glutamyltransferase (GGT), total bilirubin (TBIL), direct bilirubin, total bile acids, albumin (ALB), total protein and globulin (GLO).
  - 2) Renal function: Urea/urea nitrogen, creatinine, creatinine clearance and uric acid.
  - 3) **Blood lipids:** Total cholesterol, high density lipoprotein cholesterol (HDL), low density lipoprotein cholesterol (LDL) and triglycerides (TG).
  - 4) Electrolytes: Potassium, sodium, chloride, phosphorus, magnesium and calcium.
  - 5) Cardiac function: Creatine kinase (CK) and creatine kinase isozyme (CKI).
  - 6) **Blood glucose:** Fasting blood glucose (GLU).
  - Blood biochemistry test at screening visit should be completed within 7 days prior to the first dose, and abnormal test parameters with clinical significance can be re-tested once within 7 days as needed.
- **8.** Coagulation: Prothrombin time, activated partial thromboplastin time, fibrinogen quantification and international normalized ratio. Coagulation test at screening visit should be completed within 7 days prior to the first dose, and abnormal test parameters with clinical significance can be re-tested once within 7 days as needed.
- 9. Vital signs: Body temperature, blood pressure, heart rate and respiration. For D1 and C1D1, vital signs will be measured within 1 h pre-dose and at 10 h (± h) pos t-dose on D1 and C1D1; at other visits, vital signs will be measured according to the visit time window. If there are corresponding clinical symptoms at other time, vital signs should also be measured, and the data should be recorded.

10. 12-lead ECG: Measurements will be performed after resting in supine position, and the data (PR, QRS, QT and QTcF) will be recorded. For D1 and C1D1, ECG will be performed within 1 h pre-dose and at 10 h (± h) post -dose on D1 and C1D1; for C1D21, ECG will be performed within 0.5 h pre-dose and at 2 h (± 5 min), 4 h (± 5 min), 6 h (± 20 min), 8 h (± 30 min) and 24 h (± h, pre -dose on C2D1) post-dose on C1D21; at other visits, ECG will be performed according to the visit time window. If there are corresponding clinical symptoms at other time, ECG should also be performed, the data should be recorded, and the ECG results should be kept.

11. Physical examination: Assessments will be performed per organ and system. At screening, a comprehensive physical examination will be performed, including body height, body weight, body mass index (BMI), general condition, nervous system, head and neck, lymph nodes, skin, mucosa, chest, abdomen, four limbs and spine; at other visits, only a simple physical examination will be performed, which includes but is not limited to body weight, BMI, general condition, skin and any abnormal signs of concern at the investigator's discretion.

# 12. Pregnancy-related tests:

- 1) For women of childbearing potential, human chorionic gonadotropin (HCG) will be tested. Blood HCG pregnancy test at screening visit should be completed within 7 days prior to the first dose.
- 2) For women ≥40 to <60 years of age and at least 12 months post-menopausal, follicle stimulating hormone, estradiol and luteinizing hormone will be tested; if necessary, anti-Mullerian hormone can be tested additionally. This test will be performed at screening only.
- 3) For men and women ≥60 years of age, a pregnancy-related test is not required.
- 13. Echocardiography: Left ventricular ejection fraction (LVEF). During treatment, echocardiography will be performed at the same frequency with tumor assessment, i.e., echocardiography will be performed at the end of the 1st cycle, and the time window is ±1 day after the end of the cycle. After that, echocardiography will be performed every 2 cycles with a time window of ±7 days from the end of every 2 cycles.
- 14. Serum etiology test: Human immunodeficiency virus antibody (HIV-Ab), hepatitis B surface antigen (HbsAg), hepatitis B virus (HBV)-DNA (as needed), hepatitis C virus antibody (HCV-Ab) and hepatitis C virus (HCV)-RNA (as needed). Serum etiology test at screening visit should be completed within 14 days prior to the first dose.

